3.10 Blinding

Blinding will exist at the level of the patient and the investigator who will record the data postoperatively, regarding the surgical technique applied. There will be no blinding at the level of the surgeon and the anesthesiologist.

3.11 Data

The following data will be recorded:

- Demographics (Gender, Age, Weight, Height, ASA)
- Hemorrhoid Grade
- Operation type
- Anesthesia type
- Operative time
- Mobilization time after the anesthesia administration
- Occurrence of adverse effects
- Level of pain based on the VAS scale (0-10) at 12 hours postoperatively.
- Time of onset of oral feeding
- Postoperative use of additional analgesia .
- Postoperative time that the patient can be safely discharged
- Complications occurring at 7 days postoperatively
- Postoperative return to work time
- Remission of symptoms, at 1 month postoperatively
- Complications occurring at 1 year postoperatively
- Disease recurrence at 1 year postoperatively
- Satisfaction level at 1 year postoperatively
- SF-36 questionnaire, preoperatively, at 1 month and 1 year postoperatively

3.12 Discharge Criteria

The patient will be discharged, when it is ensured that is medically safe to be released. In particular, as the exit time of the patient, will be regarded the time that the patient will fulfill the Clinical Discharge Criteria. More specifically, the patient should meet the following : steady vital signs, be oriented, without nausea or vomiting, mobilized with a steady gait, without a significant bleeding²⁸.

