2. INTRODUCTION

2.1 Literature

Surgical operations for the treatment of perianal diseases are a major part of all elective surgical cases. The reduction in the hospitalization time of patients undergoing surgical procedures for benign perianal diseases is to the benefit of both the patient and healthcare provider¹. The importance of 'one day' surgical operations lies in the fact that the patient returns directly to his social and working environment, while the number of occupied hospital beds and the total hospitalization costs are reduced. A typical example is the goal set by NHS, where the 75% of the scheduled operations should consist of 'one day' operations¹. In order to achieve this goal, several obstacles should be dealt with, including the implementation of more efficient and safe surgical techniques. Therefore, this would be associated with a decrease in the operation time, early recovery and faster hospital discharge.

Hemorrhoids is one of the most common benign perianal diseases. According to a recent prospective study² of 976 patients, 38.93% of them suffered from hemorrhoids, with 8.16% and 0.53% being Grade III and IV, according to Goligher classification, respectively. The percentage of the symptomatic patients was, also, significant (44.74%). Symptomatic hemorrhoids, includes bleeding, pruritus, pain, poor hygiene and the presence of palpable hemorrhoid nodules.

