2.2 Research Group Experience

In a prospective 4-year study with a total of 90 patients²², the immediate post-operative and long-term course of patients undergoing DG-HAL hemorrhoid artery ligation was investigated. Totally, 64.4% of the included patients was discharged from the hospital, within 24 hours of the operation, 4.4% of patients needed additional analgesic treatment in the next 24 hours, while only 6.6% developed disease recurrence, one year after the operation. Additionally, a prospective randomized study of our clinic, compared pudendal nerve block and local anesthesia in 120 patients who underwent ultrasound scissors hemorrhoidectomy. A statistically significant lower rate of additional postoperative analgesic treatment was observed in the pudendal nerve block, while the level of postoperative pain, calculated on the Visual Analogue Scale (VAS scale), on the operative day was higher in the group of local anesthesia (5.1 vs. 2.2 $p < 0.001$)²³.

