3.7 Secondary endpoints

The secondary endpoints of the present study are:

- Operative time. Measurement unit: minutes. Time Frame: Intraoperative period
- Postoperative mobilization time. Measurement unit: hours. Time Frame: Postoperative period up to hospital discharge. Maximum time frame 24 hours
- Postoperative pain level at 12 hours after surgery, quantified with the use of the VAS scale. Time Frame: 12 hours postoperatively
- Onset of oral feeding. Measurement unit: hours. Time Frame: Postoperative period up to hospital discharge. Maximum time frame 24 hours
- Difference in the rates of adverse effects during hospitalization:
 - Hypotension. Occurrence of postoperative hypotension. If such an episode occurs, then it will be defined as=1 'YES' If such an episode does not occur, then it will be defined as=0 'NO'. Time Frame: Postoperative period up to hospital discharge. Maximum time frame 24 hours

- Nausea. Occurrence of postoperative nausea. If such an episode occurs, then it will be defined as=1 'YES' If such an episode does not occur, then it will be defined as=0 'NO'. Time Frame: Postoperative period up to hospital discharge. Maximum time frame 24 hours
- Vomiting. Occurrence of postoperative vomiting. If such an episode occurs, then it will be defined as=1 'YES' If such an episode does not occur, then it will be defined as=0 'NO'. Time Frame: Postoperative period up to hospital discharge. Maximum time frame 24 hours
- Headache. Occurrence of postoperative headache. If such an episode occurs, then it will be defined as=1 'YES' If such an episode does not occur, then it will be defined as=0 'NO'. Time Frame: Postoperative period up to hospital discharge. Maximum time frame 24 hours
- Urinary retention. Occurrence of postoperative urinary retention. If such an episode occurs, then it will be defined as=1 'YES' If such an episode does not occur, then it will be defined as=0 'NO'. Time Frame: Postoperative period up to hospital discharge. Maximum time frame 24 hours
- Bleeding at the operative site. Occurrence of postoperative bleeding at the operative site. If such an episode occurs, then it will be defined as=1 'YES' If such an episode does not occur, then it will be defined as=0 'NO'. Time Frame: Postoperative period up to hospital discharge. Maximum time frame 24 hours
- Postoperative time that the patient can be safely discharged. Measurement unit: hours. Time Frame: Postoperative period up to hospital discharge. Maximum time frame 48 hours

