3.13 Follow up

One week after the operation, the patient will be summoned to reply for any postoperative complications, the return to work time, and the current pain level. One month postoperatively, the patient will be asked about the remission of the symptoms. One year after the operation, the patient will be examined for disease recurrence and will be asked about the overall satisfaction regarding the operation.

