- Postoperative time that the patient can be safely discharged. Measurement unit: hours. Time Frame: Postoperative period up to hospital discharge. Maximum time frame 48 hours
- Complications occurring at 7 days postoperatively:
 - Pain on the basis of the VAS scale. Postoperative pain level at 7 days after surgery, quantified with the use of the VAS scale. Time Frame: 7 days postoperatively
 - Oedema at the operative site. Occurrence of postoperative oedema at the operative site. If such an episode occurs, then it will be defined as=1 'YES' If such an episode does not occur, then it will be defined as=0 'NO'. Time Frame: 7 days postoperatively
 - Hematoma at the operative site. Occurrence of postoperative hematoma at the operative site. If such an episode occurs, then it will be defined as=1 'YES' If such an episode does not occur, then it will be defined as=0 'NO'. Time Frame: 7 days postoperatively
 - Infection at the operative site. Occurrence of postoperative infection at the operative site. If such an episode occurs, then it will be defined as=1 'YES' If such an episode does not occur, then it will be defined as=0 'NO'. Time Frame: 7 days postoperatively
 - Stenosis at the operative site. Occurrence of postoperative stenosis at the operative site. If such an episode occurs, then it will be defined as=1 'YES' If such an episode does not occur, then it will be defined as=0 'NO'. Time Frame: 7 days postoperatively
- Postoperative return to work time. Measurement unit: days. Time Frame: Postoperative period up to 1 month
- Complications occurring at 1 year postoperatively:
 - Pruritus. Occurrence of postoperative pruritus at the operative site. If such an episode occurs, then it will be defined as=1 'YES' If such an episode does not occur, then it will be defined as=0 'NO'. Time Frame: 1 year postoperatively
 - Mucosal proptosis. Occurrence of postoperative mucosal proptosis at the operative site. If such an episode occurs, then it will be defined as=1 'YES' If such an episode does not occur, then it will be defined as=0 'NO'. Time Frame: 1 year postoperatively
 - Perianal nodules. Occurrence of postoperative perianal nodules. If such an episode occurs, then it will be defined as=1 'YES' If such an episode does not occur, then it will be defined as=0 'NO'. Time Frame: 1 year postoperatively

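### A shorter time to safe discharge cannot be shown to be free of more post-discharge events: unplanned return is not a planned item, and six adverse effects stop being counted at discharge

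*Protocol*

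**What the plan says.** Protocol 3.7 lists the endpoint as "Postoperative time that the patient can be safely discharged. Measurement unit: hours. Time Frame: Postoperative period up to hospital discharge. Maximum time frame 48 hours", and SAP 3.2 repeats it. Protocol 3.12 sets the clock: "as the exit time of the patient, will be regarded the time that the patient will fulfill the Clinical Discharge Criteria". The criteria are "steady vital signs, be oriented, without nausea or vomiting, mobilized with a steady gait, without a significant bleeding". SAP 5.3 compares continuous variables by t-test.

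The arms differ in anaesthesia as well as technique: spinal in the Doppler arm (Protocol 3.4), pudendal block with sedation in the experimental arm (Protocol 3.5).

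Six in-hospital adverse effects, among them "Occurrence of postoperative urinary retention" and operative-site bleeding, share a time frame that ends at discharge and is capped at 24 hours. The 7-day list holds pain, oedema, hematoma, infection and stenosis. Reoperation is read at 1 year.

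Under Protocol 3.13, at one week "the patient will be summoned to reply for any postoperative complications, the return to work time, and the current pain level". At one month that section asks about symptom remission. No endpoint list, data list (Protocol 3.11) or follow-up question names readmission, an emergency visit or any other unplanned return.

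**The concern.** The endpoint's name carries a safety claim, but nothing measured afterwards tests it. Protocol 2.1 argues for efficient and safe techniques on the ground that "this would be associated with a decrease in the operation time, early recovery and faster hospital discharge", so a shorter time is likely to be read as support for that rationale. Because the anaesthetic differs by arm, a difference in discharge time is plausible whatever the surgical technique does.

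Two things follow. First, a patient who meets the criteria early and comes back on day 2 with bleeding or retention, treated without an operation, contributes a short discharge time and has no listed endpoint in which the return appears. Second, the in-hospital counts share their end point with the endpoint they would have to balance: the earlier a patient is discharged, the sooner counting stops. Lower counts of these six effects in the earlier arm could then partly reflect shorter observation.

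**Working it through.** **What is observed, and until when (Protocol 3.7, SAP 3.2)**

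| Event | Window | On the 7-day list |
|---|---|---|
| Operative-site bleeding, urinary retention | to discharge, at most 24 h | no |
| Nausea, vomiting, headache, hypotension | to discharge, at most 24 h | no |
| Pain (VAS) | at 12 h and at 7 days | yes |
| Oedema, hematoma, infection, stenosis | 7 days | yes |
| Reoperation | 1 year | no |
| Unplanned return, any cause | none | no |

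**Length of observation.** Let T be the discharge time in hours. The counted window for the first two rows is W = min(T, 24).

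- If T_A < T_B ≤ 24, then W_A/W_B = T_A/T_B, which is below 1. With the same constant, low event rate in both arms (an assumption), expected counts fall in roughly that ratio. Events that cluster soon after surgery would be affected less.
- If both times exceed 24 h, the windows are equal and this part disappears. Discharge time itself runs to 48 h, so an event in hospital after 24 h is not counted either.
- Discharge before 24 h is realistic: in the group's own Doppler series "64.4% of the included patients was discharged from the hospital, within 24 hours of the operation" (Protocol 2.2).
- Day 7 is 168 h. For these six effects at least 168 − 24 = 144 h, or 144/168 = 86%, lies outside the window for every patient.

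**Sample size, as context.** With 72.5%, 90%, a 10-point margin, α = 2.5% read as one-sided and power 80%:

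n = (1.960 + 0.842)² × (0.725×0.275 + 0.90×0.10) / (0.90 − 0.725 + 0.10)² = 7.849 × 0.2894 / 0.0756 = 30.03

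The stated 30 per arm reproduces (31 if rounded up). It rests on the primary endpoint, so a new descriptive item does not change it.

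**What a return item could show with 30 per arm.** The documents give no return rate, so the rates below are assumptions.

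- Exact two-sided 95% upper limit for 0/30: 1 − 0.025^(1/30) = 0.116, i.e. 11.6%.
- Zero returns in both arms: the Wilson upper limit is 3.84/(30 + 3.84) = 0.114, so the Newcombe interval for the difference is about −11.4 to +11.4 points.
- Fisher's exact test: 0/30 against 5/30 gives p = 0.052; 0/30 against 6/30 gives p = 0.024.
- Power at two-sided 5%, from Φ{[d√n − 1.96√(2p̄(1−p̄))] / √(p₁(1−p₁) + p₂(1−p₂))}, where d is the absolute difference and p̄ the mean of the two rates:

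| Assumed rates | Power, 30 per arm | n per arm for 80% |
|---|---|---|
| 2% vs 5% | 9% | 588 |
| 5% vs 10% | 11% | 435 |
| 2% vs 10% | 25% | 138 |
| 5% vs 15% | 25% | 141 |
| 5% vs 20% | 42% | 76 |
| 2% vs 20% | 61% | 47 |

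The item can therefore support counts with intervals, but not a test of equal safety.

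**The case against.** The best defence has three parts.

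*The endpoint is not discretionary.* It is the time at which fixed criteria are met, the same in both arms. Data are collected by an independent researcher, and the investigator recording postoperative data is blinded to technique. Nobody is sent home early to shorten the clock. This stands, and it makes the timing comparable. It does not show that patients who meet the criteria stay free of later events.

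*Early trouble would show elsewhere.* A reader might infer that reoperation is the only related item. It is not. The one-week question is open to any complication, 7-day pain, hematoma and infection are compared endpoints, and return to work and SF-36 at 1 month would reflect a bad early course. This stands in part. The compared 7-day list is closed at five items, so an answer about bleeding or retention has no prespecified comparison to enter. The one-week pain item is the level at that contact, so pain that brought a patient back on day 2 and settled by day 7 leaves no trace. Reoperation misses returns managed without surgery.

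*The added item would be too sparse to verify safety.* This is correct at 30 per arm, and the fix is limited to description for that reason. It does not justify leaving the item out, since returns are hard to reconstruct reliably afterwards.

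**Conclusion.** The gap is real and minor. Discharge time is compared without a prespecified count of unplanned returns. Bleeding, retention, nausea, vomiting, headache and hypotension are followed only to discharge or 24 hours, whichever comes first. A shorter time therefore cannot be shown to be free of more post-discharge events, and below 24 hours the earlier arm is observed for less time. The size of any resulting difference cannot be derived, because the documents give neither discharge times by arm nor a return rate.

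A reader might go further and infer that an arm with more readmissions would be reported as the better one. The documents do not support that. The primary endpoint is remission at 1 month, discharge time is one of 26 secondary items by my count, and no rule uses it to declare a better arm. The earlier arm would look better on that line only.

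Nor should illustrative figures be read as evidence of harm. Applying 64.4% to all 60 patients gives about 39 home within 24 hours (0.644 × 60 = 38.6), but the rate comes from a series of the Doppler technique alone. An assumed return risk of 5% to 10% gives a 79% to 96% chance of at least one return in 30 (1 − 0.95³⁰, 1 − 0.90³⁰). That only restates the assumption and says nothing about a difference between arms.

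**What to change.** 1. In Protocol 3.7, 3.11 and 3.13 and SAP 3.2, add: unplanned return to hospital or emergency care since discharge (1 YES / 0 NO, with date and reason, the reasons to include bleeding, retention, vomiting and pain). Ask it at the existing 1-week and 1-month contacts and check it against the patient chart, which is already a data source.
2. Count post-discharge bleeding and urinary retention to day 7 in both arms, so that the window no longer depends on discharge time. The in-hospital counts can stay as they are, labelled as such.
3. Report the counts by allocated arm beside discharge time, with a 95% CI for the difference, and state that they are descriptive. Use a score-based interval, because a simple Wald interval collapses to zero width if both counts are zero. SAP 5.3 bases its estimates on a per-protocol analysis, so say there that this item is reported by allocation.

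The cost is one question at two existing contacts, a chart check at a single site and a few lines of wording. Sample size, treatment and discharge criteria are untouched. The downside is one more low-event endpoint with little power, which will not prove equal safety.

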3.13 Follow up

One week after the operation, the patient will be summoned to reply for any postoperative complications, the return to work time, and the current pain level. One month postoperatively, the patient will be asked about the remission of the symptoms. One year after the operation, the patient will be examined for disease recurrence and will be asked about the overall satisfaction regarding the operation.

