- Complications occurring at 7 days postoperatively:
 - Pain on the basis of the VAS scale. Postoperative pain level at 7 days after surgery, quantified with the use of the VAS scale. Time Frame: 7 days postoperatively
 - Oedema at the operative site. Occurrence of postoperative oedema at the operative site. If such an episode occurs, then it will be defined as=1 'YES' If such an episode does not occur, then it will be defined as=0 'NO'. Time Frame: 7 days postoperatively
 - Hematoma at the operative site. Occurrence of postoperative hematoma at the operative site. If such an episode occurs, then it will be defined as=1 'YES' If such an episode does not occur, then it will be defined as=0 'NO'. Time Frame: 7 days postoperatively
 - Infection at the operative site. Occurrence of postoperative infection at the operative site. If such an episode occurs, then it will be defined as=1 'YES' If such an episode does not occur, then it will be defined as=0 'NO'. Time Frame: 7 days postoperatively
 - Stenosis at the operative site. Occurrence of postoperative stenosis at the operative site. If such an episode occurs, then it will be defined as=1 'YES' If such an episode does not occur, then it will be defined as=0 'NO'. Time Frame: 7 days postoperatively
- Postoperative return to work time. Measurement unit: days. Time Frame: Postoperative period up to 1 month
- Complications occurring at 1 year postoperatively:
 - Pruritus. Occurrence of postoperative pruritus at the operative site. If such an episode occurs, then it will be defined as=1 'YES' If such an episode does not occur, then it will be defined as=0 'NO'. Time Frame: 1 year postoperatively
 - Mucosal proptosis. Occurrence of postoperative mucosal proptosis at the operative site. If such an episode occurs, then it will be defined as=1 'YES' If such an episode does not occur, then it will be defined as=0 'NO'. Time Frame: 1 year postoperatively
 - Perianal nodules. Occurrence of postoperative perianal nodules. If such an episode occurs, then it will be defined as=1 'YES' If such an episode does not occur, then it will be defined as=0 'NO'. Time Frame: 1 year postoperatively
 - Constipation. Occurrence of postoperative constipation. If such an episode occurs, then it will be defined as=1 'YES' If such an episode does not occur, then it will be defined as=0 'NO'. Time Frame: 1 year postoperatively

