5.3 Statistical Procedures

The statistical estimations of this study will be based on a per protocol analysis. Prior to any computation, all data will be submitted to a Shapiro-Wilk normality test.

Continuous variables will be compared on the basis of an independent samples t-test, whereas for categorical variables, the Pearson chi-square test will be applied.

The effect of the various patient characteristics on the primary and secondary endpoint will be evaluated by a regression analysis. More specifically, a multiple linear and a logistic regression will be used for continuous and categorical variables, respectively.

Regression analysis will be applied to all distinct endpoints. The validity of the linear regression model will be confirmed by the assessment of the following assumptions:

- Independence of observations, assessed by the Durbin-Watson test
- Linear relationship between the dependent variable and each of the independent variables and between the dependent variable and all the independent variables, collectively.
- Homoscedasticity of the data
- Multicollinearity of the data
- Absence of significant outliers, high leverage points or highly influential points
- Normal distribution of the residuals

A Forward model will be introduced in our multiple linear regression analysis. The proportion of variance explained by our model will be represented by R square. The statistical significance of our model will be evaluated by the F-test. The effect of each independent variable on the dependent outcome will be provided by the respective coefficient and the 95%CI.

Similarly, a Forward model will be applied in our logistic regression analysis. The following assumption will be tested:

- Independence of observations and mutual exclusive and exhaustive categories
- Linear relationship between any continuous independent variable and the logit transformation of the dependent variable

The explained variance will be presented by the Cox & Snell R square and Nagelkerke R square test. The percentage of the correctly classified observations will be also estimated. The statistical significance of each variable will be calculated by the Wald test. The odds ratios of each variable will be also estimated, alongside the respective 95%CI.

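### Return-to-work time has a window of up to 1 month, but no contact after week 1 is scheduled to capture it, and the SAP has no rule for patients still off work

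*Protocol*

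**What the plan says.** Protocol 3.7 lists the endpoint as "Postoperative return to work time. Measurement unit: days. Time Frame: Postoperative period up to 1 month". SAP 3.2 gives it the same unit and window.

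Protocol 3.13 describes three contacts:
- **One week:** "the patient will be summoned to reply for any postoperative complications, the return to work time, and the current pain level".
- **One month:** "One month postoperatively, the patient will be asked about the remission of the symptoms".
- **One year:** "One year after the operation, the patient will be examined for disease recurrence and will be asked about the overall satisfaction regarding the operation".

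The data list in Protocol 3.11 contains "Postoperative return to work time" with no time of collection. The same list gives explicit times for another item that 3.13 leaves out: "SF-36 questionnaire, preoperatively, at 1 month and 1 year postoperatively".

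On analysis, SAP 5.3 says "Continuous variables will be compared on the basis of an independent samples t-test" and adds multiple linear regression for continuous endpoints. SAP 5.2 deals with missing values by multiple imputation and regards less than 10% missing as acceptable. Neither section mentions censoring or a time-to-event method.

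**The concern.** The window and the collection point do not match. A patient who goes back to work on day 12 falls inside the endpoint's window, but at the only scheduled question can say no more than that the return has not yet happened. The SAP does not say what is then entered in the database. It could be a blank, which is later imputed, or it could be 7 days.

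The values at risk are the long ones. A blank here depends on the unobserved value itself, because it arises only when the time exceeds about 7 days. Imputation based on patients with a recorded time would be centred on early returners and would tend to assign times that are too short. A cap at day 7 keeps the patient in the analysis but discards the length of the delay.

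Early return to work is one of the benefits that the introduction (Protocol 2.1) gives for one-day surgery, so this endpoint bears on the trial's rationale, although it is secondary.

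**Working it through.** **Setting the sections side by side.** The endpoint window ends at 1 month, about day 30. The only scheduled question comes at about day 7. That leaves 30 − 7 = 23 days of the window with no scheduled capture. No section of either document places the question at a later contact.

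**Plan's own figure.** There is none to reproduce: the documents give no expected return-to-work time, spread or arm difference. The one input taken from them is 30 patients per arm (Protocol 3.8, SAP 5.1). Everything else below is assumed.

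**Share not back by day 7.** Assume log-normal times with median m days and log-SD s. Then

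share = 1 − Φ( ln(7/m) / s ).

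- m = 2, s = 0.5: ln(3.5) = 1.253; 1.253/0.5 = 2.51; share = 0.6%, about 1%.
- m = 7, any s: ln(1) = 0; share = 50%.
- m = 14, s = 0.5: ln(0.5) = −0.693; −0.693/0.5 = −1.39; share = 92%.

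**Effect on the comparison.** Simulated trials with 30 per arm and a two-sided t-test at 0.05 (6,000 trials per row; simulation error in power up to about one percentage point), analysed in three ways: times followed to day 30; all times capped at day 7; only patients back by day 7. Each of the last two columns gives these three results in that order.

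| Medians (days) | log-SD | Not back by day 7, per arm | Mean difference in days: to day 30 / capped / returners only | Power: to day 30 / capped / returners only |
|---|---|---|---|---|
| 2 vs 3 | 0.5 | 1%, 5% | 1.1 / 1.1 / 0.9 | 83% / 84% / 79% |
| 2 vs 3 | 0.7 | 4%, 11% | 1.3 / 1.0 / 0.7 | 51% / 56% / 43% |
| 4 vs 6 | 0.5 | 13%, 38% | 2.3 / 1.3 / 0.8 | 83% / 84% / 47% |
| 4 vs 6 | 0.7 | 21%, 41% | 2.5 / 1.1 / 0.6 | 52% / 55% / 23% |
| 7 vs 10 | 0.5 | 50%, 76% | 3.3 / 0.7 / 0.5 | 74% / 58% / 10% |
| 7 vs 10 | 0.7 | 50%, 69% | 3.3 / 0.7 / 0.4 | 44% / 37% / 9% |
| 10 vs 14 | 0.5 | 76%, 92% | 4.1 / 0.3 / 0.3 | 69% / 32% / 3% |
| 10 vs 14 | 0.7 | 69%, 84% | 3.7 / 0.4 / 0.3 | 42% / 24% / 5% |

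Three things follow.
- With fast recovery, little is lost.
- With medians of 4 vs 6 days, capping costs no power but roughly halves the estimated difference, and dropping late returners costs a good deal of power.
- With medians of 7 days or more, both handlings lose most of the difference.

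**Against the SAP's 10% level.** If late returners are blanks, the missing share over both arms is the average of the two shares. For 2 vs 3 days at log-SD 0.5 it is (0.6% + 4.5%)/2 = 2.6%, inside the limit. For 4 vs 6 days at log-SD 0.5 it is (13% + 38%)/2 = 25.5%, well outside it.

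**The case against.** A reader might infer that every return after day 7 will be lost. The documents do not support that. Section 3.13 is not a complete schedule: it names only symptom remission at 1 month, although the SF-36 is also due then under 3.7 and 3.11. Staff may in practice ask about work again at that contact, and the endpoint's own window suggests that later returns were meant to count. This stands as far as it goes. It does not remove the mismatch, because for the SF-36 another section supplies the time points, and for return to work none does.

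A reader might also infer that the comparison is necessarily biased toward no difference. That needs a true difference between arms, and the documents neither state nor hypothesise one for this endpoint. If the arms have the same distribution, cutting off at day 7 affects both alike.

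Finally, a reader who considers only medians of a week or more would conclude that the endpoint is ruined. Shorter medians are equally consistent with the documents, which describe minimally invasive surgery with early discharge as the aim, and under these the loss can be small. This stands as well, and is why the size is given as a wide range.

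**Conclusion.** The point holds as a mismatch between sections. The endpoint runs to 1 month, the question is scheduled only at one week, and the SAP has no rule for a patient who has not yet returned. This follows from the text and needs no assumption. What it would do to the result does need assumptions: that sites follow 3.13 literally, that the arms truly differ, and some distribution of times. Under assumed log-normal times with medians of 2 to 14 days and log-SD 0.5 to 0.7, the share of an arm still off work at day 7 runs from about 1% to 92%, and the effect from negligible to severe. Nothing in the documents narrows that range. It concerns one secondary endpoint. It should be corrected because the correction is easy, and late return dates may be hard to recover reliably afterwards.

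**What to change.** Reconcile Protocol 3.7, 3.11 and 3.13. In 3.13, ask for the date of return to work again at the existing 1-month contact for anyone not back at week 1, and put the same collection times against the item in 3.11.

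In SAP 5.2 and 5.3, state that patients still off work at 1 month are treated as censored at that date, not as missing, and name a comparison that respects this. A log-rank or rank-based test would do; another method that handles censoring would serve equally well.

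The cost is one extra question at a contact already planned and one line in the SAP. No new visit, additional patients or change to the primary analysis is needed.
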